Our goal is to create an AI-assisted diagnostic tool that can be easily integrated into clinical workflows, offering a cost-effective and accessible solution for osteoporosis screening.

• **Objectives:** The primary objective is to curate a comprehensive dataset of X-ray images sourced from publicly available domains and local health facilities, encompassing a diverse representation of patient demographics, geographic locations, and equipment variations. Building upon this dataset, we seek to develop a robust artificial intelligence model capable of prediction of bone mineral density from X-ray images.

The specific objectives of the study are:

- a) To develop a deep learning convolutional neural network (CNN) model that can accurately predict Bone Mineral Density (BMD) values from Xray images, using both prospective and retrospective data collection methods.
- b) To validate the AI model's performance on a diverse dataset encompassing a broad demographic, including variables such as age, gender, height, weight, menopausal status, and the presence of comorbidities like cardiovascular disease and diabetes.
- c) To evaluate the model's performance using a range of metrics, including Area Under the Precision-Recall Curve (AUPRC), accuracy, Mean Absolute Error (MAE), and Pearson Correlation Coefficient (PCC), ensuring its robustness in predicting BMD.
- d) To assess the usability and interpretability of the AI model's output by healthcare professionals, determining its integration into clinical practice and its impact on the diagnostic workflow efficiency.
- e) To measure the generalizability and adaptability of the model across various healthcare settings, ensuring the AI system's reliability on X-ray images from different populations and regions.

- f) To investigate the model's potential in enhancing early detection and treatment planning for osteoporosis by providing a non-invasive, cost-effective tool for BMD estimation, potentially leading to better patient management and outcomes.
- g) To assess the AI model's role as a decision support tool in determining the necessity for additional diagnostic procedures, such as DEXA scans, thereby optimizing patient care pathways and potentially reducing healthcare costs.

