- d) **Methods of Data Collection:** The following fields will be recorded in the data collection for this study:
 - Patient ID (unique identification number)
 - Date & time of the data input
 - Age
 - Gender
 - Phone number
 - X-ray image (hip or spine)

- DEXA scan result
- BMI
- Menopausal status
- Diabetes
- Cardiovascular disease and other clinical covariates

The X-ray images, and DEXA scan result of the subjects along with the relevant clinical covariates will be used to design the algorithms. The standard test status and the corresponding result will be used as the ground truth for our detection algorithm.

e) **Data Interpretation:** Upon the conclusion of data collection, exploratory data analysis to assess the distribution of patients across different demographics and clinical factors, including age, gender, menopausal status, presence of cardiovascular diseases, diabetes, and their correlation with BMD values. This process will ensure a comprehensive understanding of the dataset's characteristics and the establishment of a balanced dataset that represents a wide spectrum of patient profiles.

The refined dataset will serve as the foundation for training and evaluating our AI model, specifically designed for the regressionbased prediction of BMD from X-ray images. Our AI algorithm will leverage CNN to process X-ray images and predict BMD values, aiming to identify potential cases of osteopenia, osteoporosis, and normal.

To ascertain the model's performance and its clinical applicability, we will compare the AI-generated predictions with actual BMD measurements obtained from DEXA scans. This validation process will involve collaboration with orthopedic specialists and radiologists who will review the AI predictions in the context of their clinical experience and available patient information.

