f) Statistical Analysis: Upon finalizing the dataset, our statistical analysis will concentrate on evaluating the artificial intelligence model's capability to predict BMD from X-ray images accurately. Performance metrics such as Mean Absolute Error (MAE), Pearson Correlation Coefficient (PCC), Area Under the Precision-Recall Curve (AUPRC), and accuracy will be employed to meticulously assess the model's performance. To ensure the reliability of our findings, we will implement k-fold cross-validation techniques, providing a framework for evaluating our model across various subsets of data. This approach will allow us to calculate mean values and standard deviations for each performance metric, offering a comprehensive understanding of the model's predictive accuracy and consistency. The culmination of our analysis will involve a comparative review of different CNN architectures and training methodologies to determine the most effective strategy for BMD prediction from X-ray images.

Utilization of Results: The study results will play a crucial role in the development and evaluation of an automatic BMD prediction algorithm for osteoporosis screening. The algorithm's primary objectives are:

a) BMD Prediction: To accurately predict BMD values from X-ray images, facilitating an automated assessment tool for early detection of osteoporosis and osteopenia. This tool aims to bridge the gap in accessibility to BMD testing, especially in resource-limited settings.

b) Clinical Decision Support: To aid healthcare professionals by providing automated BMD assessments, enhancing their ability to make informed decisions regarding patient care. The model's predictions can help prioritize patients who need further testing or intervention, streamlining the diagnostic process.

c) Correlation Analysis: To explore and identify significant relationships between BMD or osteoporosis and collected clinical covariates such as age, gender, menopausal status, cardiovascular diseases, and diabetes. This analysis aims to enhance understanding of the factors influencing bone health, contributing to personalized and more precise osteoporosis risk assessment and management strategies.

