d) Data Management for Bone Health Research: To enable systematic storage and organization of X-ray images along with their corresponding BMD values and clinical data. This will not only support future research in the field of bone health but also ensure the privacy and security of patient data throughout the process.

These outcomes are poised to significantly enhance the efficiency and accuracy of osteoporosis screening, providing valuable support to healthcare professionals in Bangladesh.

- **Facilities:** For the collection of data for our thesis on predicting Bone Mineral Density (BMD) from X-ray images, no extra facilities are necessary beyond those already available in the radiology departments (e.g., X-ray imaging, DEXA scan, and data storage capabilities).
- Approval / Forwarding of the Head of Department / Institute / IRB: A forwarding letter from the Department of Biomedical Engineering, Bangladesh University of Engineering and Technology (BUET) is attached.
- **Flow Chart:** The data collection activity and the corresponding timeline is described in the Gantt chart below:

No.	Work/Activities	Months			
		1	2	3	4
1	Initial algorithm with publicly available data				
2	Collection of images, reports and metadata				
3	Homogenization and organization of data				
3	Data processing and analysis				

- Ethical Implications: The proposed retrospective/prospective study based on medical records is designed to develop and evaluate the diagnostic performance of AI algorithms that will predict BMD from X-ray images. The study poses minimal to no risk to the subjects according to the HHS (USA) definition.
- References:
 - O. Johnell and J. A. Kanis, "An estimate of the worldwide prevalence and disability associated with osteoporotic fractures," Osteoporos. Int., vol. 17, no. 12, pp. 1726–1733, Dec. 2006, doi: 10.1007/s00198-006-0172-4.
 - L. Sànchez-Riera et al., "The global burden attributable to low bone mineral density," Ann. Rheum. Dis., vol. 73, no. 9, pp. 1635–1645, Sep. 2014, doi: 10.1136/annrheumdis-2013-204320.
 - A. S. Nazrun, M. N. Tzar, S. A. Mokhtar, and I. N. Mohamed, "A systematic review of the outcomes of osteoporotic fracture patients after hospital discharge: morbidity, subsequent fractures, and mortality," Ther. Clin. Risk Manag., vol. 10, pp. 937–948, Nov. 2014, doi: 10.2147/TCRM.S72456.

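### Objective e) promises generalizability across settings and regions, but the only stated validation is k-fold on one dataset, source and device are not listed fields, and the sources are described inconsistently

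*Protocol*

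**What the plan says.** **The aim.** In the Protocol's Objectives, item e) reads "To measure the generalizability and adaptability of the model across various healthcare settings" and continues "ensuring the AI system's reliability on X-ray images from different populations and regions". The opening paragraph of the same section also promises a dataset that varies in geography and equipment. The Introduction criticises existing work for relying on localized samples and makes generalizability a particular focus of this study.

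**The analysis.** Methodology e) says "The refined dataset will serve as the foundation for training and evaluating our AI model" and adds that "we will compare the AI-generated predictions with actual BMD measurements obtained from DEXA scans", with review by orthopedic specialists and radiologists. Methodology f) names MAE, PCC, AUPRC and accuracy, and then states: "we will implement k-fold cross-validation techniques, providing a framework for evaluating our model across various subsets of data". Each metric is to be summarised by its mean and standard deviation, and CNN architectures are then compared.

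**The data.** Methodology d) opens with "The following fields will be recorded in the data collection for this study". The list covers patient ID, date and time of entry, age, gender, phone number, X-ray image, DEXA result, BMI, menopausal status, diabetes, and cardiovascular disease with other clinical covariates. The Questionnaire Form asks whether the X-ray was done at one named facility in the last three months, and for its type, ID and date. The Flow Chart adds "Collection of images, reports and metadata" without saying what the metadata contain.

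**The concern.** An explicit objective has no stated analysis that answers it, and the variables that such an analysis needs are not among the fields to be recorded. If the plan is followed as written, the cross-validated metrics describe the source or sources that happened to be sampled. A reader of the results could still take them as evidence about other hospitals, regions and machines, because objective e) says that this was measured.

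Timing matters. Adding source and device fields before collection is cheap. Recovering them later depends on what the unspecified metadata hold, or on going back to records from which identifying information has been removed after linkage.

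**Working it through.** **Step 1. Set the objective against the stated plan (all Protocol).**

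| Part of the promise | Analysis stated in Methodology e) and f) | Variable listed in Methodology d) or the Questionnaire Form |
|---|---|---|
| Populations (age, gender, menopausal status, comorbidity) | None by subgroup, but objective b) covers it and it is feasible | Yes |
| Healthcare settings | None by setting | Only a yes/no item for one facility |
| Regions | None by region | None |
| Equipment (dataset description in Objectives) | None by device | None |

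The gap therefore concerns settings, regions and equipment, not patient characteristics.

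**Step 2. What k-fold on the pooled dataset estimates.** Methodology f) does not tie the folds to facility, region or device. With folds formed without regard to source, the patients held out come from the same sources as the patients trained on. The mean over folds is then performance on that mix of sources. The standard deviation over folds reflects patient sampling and variation in training. Neither is performance at a source absent from training. Folds could be defined by source, but that requires source to be recorded. The DEXA comparison and the specialist review name no separate source.

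**Step 3. Which sources contribute.** The sections do not agree:
- Introduction, Objectives and Facilities: local facilities or radiology departments, in the plural.
- Methodology c), retrospective phase: the database of one clinic, in the singular.
- Questionnaire Form: one named facility.
- Justifications for Informed Consent Waiver: hospitals in the plural, in a general remark on obtaining consent.
- Public images: part of the dataset in Objectives, but in the Flow Chart only under "Initial algorithm with publicly available data".

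**Step 4. Reproduce the plan's sample size.** Inputs from Methodology b): 95% confidence (Z = 1.96), precision 0.05, prevalence 0.373, sensitivity 0.911, specificity 0.689.
- N_sen = 1.96² × 0.911 × 0.089 / (0.05² × 0.373) = 334.02, rounded up to 335 (stated 335).
- N_spec = 1.96² × 0.689 × 0.311 / (0.05² × 0.627) = 525.15, rounded up to 526 (stated 526).

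Both reproduce. The calculation is for the pooled sample; no source enters it.

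**Step 5. Precision by source at the target of 600.** The half-width for specificity is 1.96 × sqrt(0.689 × 0.311 / (n × 0.627)), with n patients per source. Assumptions: equal split, the planning prevalence and specificity in every source, and all 600 patients evaluated.

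| Sources | n per source | Half-width, specificity (points) |
|---|---|---|
| Pooled | 600 | 4.7 |
| 2 | 300 | 6.6 |
| 3 | 200 | 8.1 |
| 5 | 120 | 10.5 |

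Specificity is used because it has a planning value and drives the sample size. MAE, PCC and AUPRC have no planning values and cannot be sized in this way.

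**The case against.** **A statistical analysis plan may cover it.** This is the strongest objection. Validation splits and by-source intervals are ordinary content for such a plan, and their absence from a protocol would not by itself be a finding. Nor is the sentence on k-fold false: it is offered for reliability and consistency and never claims to measure transfer between facilities. That much stands. But a later plan cannot analyse by a source or device that nobody recorded, and the data fields and contributing sources are fixed in this protocol, where they do not match objective e).

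**The field list is not exhaustive.** This is also true. The questionnaire collects items that Methodology d) omits, metadata are planned, and a retrospective image's source may be known from the database it came from. A yes on the facility item ties an image to one place. So it would be too strong to infer that by-source analysis is impossible. What can be said is that no listed field secures it, that a no on the facility item identifies no other source, and that devices appear nowhere.

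**A single-site study.** A reader might infer from the retrospective procedure and the questionnaire that only one facility contributes, so that variation between facilities could not be estimated at all. The plural wording elsewhere does not support that conclusion. The documents are ambiguous on this and need reconciling.

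**All of objective e) fails.** A reader might also infer this. It does not follow, because the population part can be examined with listed covariates.

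**Conclusion.** The concern holds for settings, regions and equipment. Followed as written, the protocol yields a measure of internal consistency, lists no field that securely identifies facility or device, and does not say consistently which sources contribute. It should be corrected before data collection. The primary objective and the arithmetic of the sample size are not affected.

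The conclusion rests on the text and not on any assumed difference between facilities. The protocol gives no between-facility variation, so the loss of performance at a new facility cannot be sized from it. What can be sized is the price of by-source reporting: about 6.6, 8.1 or 10.5 points for specificity with 2, 3 or 5 equal sources, against 4.7 pooled. The 0.05 precision is therefore met for the pooled sample but not within sources.

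**What to change.** 1. Add facility or data source, X-ray device and DEXA device to the fields in Methodology d) and to the Questionnaire Form, and extract the same items with the retrospective images. State in one place which sources contribute and whether public images enter the evaluation or only the initial algorithm. Bring the Introduction, Objectives, Methodology c), Facilities, Flow Chart, Questionnaire Form and consent-waiver text into line with it.
2. If several sources contribute, name leave-one-source-out evaluation as the analysis for objective e), with results and an interval for each source. With only two or three sources, report each one and make no claim about regions in general.
3. If only one facility contributes, restrict objective e) and the conclusions to that facility.

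**Cost.** Two or three extra fields, one rewritten paragraph, some computing, and a narrower or less favourable claim with the wider intervals shown above. No extra patients are needed if the claim is limited to the contributing sources. If only one facility contributes, keeping objective e) as worded would need DEXA-linked images from at least one more.

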The final sample size N is calculated based on the larger of the two values N_{sen} and N_{spec} . In this study, as we are using deep learning techniques, we need the medical image samples to reflect the various osteoporosis, osteopenia and normal cases. For our analysis, we assume an 95% confidence level, precision of 0.05, and prevalence of osteoporosis, p = 0.373 [8]. We estimate the sensitivity and specificity of our algorithms to be at 91.1% and 68.9% respectively (*sen* = 0.911 and *spec* = 0.689) [17]. Using these values, we obtain the sample size values: $N_{sen} = 335$ and $N_{spec} = 526$. Since $N_{spec} > N_{sen}$, the final sample size for the study will be:

$$N = N_{sen} = 526$$

We can set a target of N = 600.

c) **Procedures:** In the prospective phase of the study, data collection will be conducted within clinical settings. Eligible patients will be approached during X-ray scans and BMD tests and presented with a consent form for their consideration. Upon agreement, a unique identifier will be assigned to maintain data integrity while preserving patient anonymity. Following the consent process, patients will provide essential clinical information. Healthcare professionals will perform an X-ray or DEXA scan, and the results will be generated and collected. This approach ensures the acquisition of non-identifiable information, unique data identifiers, and informed consent directly within the clinical setting, aligning with the specific requirements of the study.

In the retrospective phase of the study, additional data will be extracted from the clinic's database. We will collect all spine and hip X-ray images and BMD reports from the radiology department. The identification and matching process will rely on patient ID, phone number, date of birth, and other shared clinical information present in both the X-ray and BMD reports. Given the retrospective nature of this approach, tracking down and obtaining consent from individual patients is not feasible. To address privacy concerns, any personally identifiable patient information will be systematically removed from the collected data. This strategy ensures compliance with privacy standards while utilizing valuable information from previous screenings. Although informed consent cannot be obtained for this specific dataset, the study will strictly adhere to ethical guidelines and prioritize patient privacy throughout the data extraction process from the clinic's database.

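### Mean and SD across an unstated number of folds is the only performance summary; that SD grows with the number of folds and is not the 95% precision of 0.05 used to size the study

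*Protocol*

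**What the plan says.** Under Methodology f) Statistical Analysis, the protocol states that "we will implement k-fold cross-validation techniques, providing a framework for evaluating our model across various subsets of data". The purpose given is to "calculate mean values and standard deviations for each performance metric", and the result is presented as a full account of how accurate and how consistent the model is. The metrics are introduced as "Performance metrics such as Mean Absolute Error (MAE), Pearson Correlation Coefficient (PCC), Area Under the Precision-Recall Curve (AUPRC), and accuracy". The number of folds is not given. No standard error, confidence interval or bootstrap for model performance appears in the protocol.

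Under Methodology b) Sample size calculation, the study is sized on a different quantity: "we assume an 95% confidence level, precision of 0.05, and prevalence of osteoporosis, p = 0.373". The performance assumptions follow: "We estimate the sensitivity and specificity of our algorithms to be at 91.1% and 68.9% respectively". The formulas give 335 for sensitivity and 526 for specificity, and the section ends: "We can set a target of N = 600".

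**The concern.** The two sections use different measures of precision. The sample size section aims at a 95% half-width of 0.05 for an estimate from the whole sample. The analysis section reports the spread of a metric between folds, each tested on only about 600/k patients. That spread depends on fold size, so the same patients and the same quality of model give a larger SD with more folds, although the overall estimate has become no less precise.

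Mean plus or minus SD is easily read as the uncertainty of the result. A reader who does so gets a figure set partly by a choice of k that the protocol does not fix, and one that cannot be set against the 0.05 target.

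**Working it through.** **Inputs.** From the sample size section: sensitivity 0.911, specificity 0.689, prevalence p = 0.373, precision c = 0.05, 95% confidence (two-sided z = 1.96), target N = 600. The number of folds is not in the protocol; k = 3, 5, 10 and 20 are assumptions that show the range.

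**1. Reproducing the plan's figures.**
- N_sen = z² × sen(1 − sen) / (c² × p) = 3.8415 × 0.081079 / (0.0025 × 0.373) = 334.01, rounded up to 335.
- N_spec = z² × spec(1 − spec) / (c² × (1 − p)) = 3.8415 × 0.214279 / (0.0025 × 0.627) = 525.13, rounded up to 526.

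Both match. A one-sided z would give about 236 and 370, which do not. So 0.05 is a two-sided 95% half-width on the whole sample.

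**2. Accuracy implied by the inputs.** Sensitivity and specificity are the sized quantities, but the analysis section does not name them; it names accuracy. Taking accuracy as two-class (osteoporosis or not): 0.373 × 0.911 + 0.627 × 0.689 = 0.3398 + 0.4320 = 0.772.

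**3. Whole-sample 95% half-width at N = 600**, from 1.96 × sqrt(q(1 − q)/n):
- Accuracy, n = 600: 1.96 × 0.0171 = 0.034.
- Sensitivity, n = 600 × 0.373 = 223.8: 1.96 × 0.0190 = 0.037.
- Specificity, n = 600 × 0.627 = 376.2: 1.96 × 0.0239 = 0.047.

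None of these depends on k.

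**4. Expected between-fold SD from test-set sampling alone**, from sqrt(q(1 − q)/(n/k)), with equal, stratified folds. For accuracy at k = 5: sqrt(0.1761/120) = 0.038. At k = 10: sqrt(0.1761/60) = 0.054.

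| Metric | k = 3 | k = 5 | k = 10 | k = 20 | 95% half-width, any k |
|---|---|---|---|---|---|
| Accuracy | 0.030 | 0.038 | 0.054 | 0.077 | 0.034 |
| Sensitivity | 0.033 | 0.043 | 0.060 | 0.085 | 0.037 |
| Specificity | 0.041 | 0.053 | 0.075 | 0.107 | 0.047 |

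The ratio of fold SD to half-width is sqrt(k)/1.96, that is 0.88, 1.14, 1.61 and 2.28. The two are equal at k = 1.96² = 3.84, so from four folds upwards the expected SD is the larger. Going from 5 to 20 folds doubles it.

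**5. Stability of the SD itself.** A binomial simulation (4,000 runs, 376 patients without osteoporosis) gave a mean fold SD for specificity of 0.050 at k = 5 and 0.073 at k = 10, slightly below the formula, as expected for a small number of folds. At k = 5 the central 95% of simulated SDs ran from 0.018 to 0.089, so a single observed value says little.

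**The case against.** The strongest reply is that this is only a missing detail. The protocol never calls the fold SD a standard error or a confidence interval, a fold SD is a legitimate description of consistency, and the choice of k and of interval methods is commonly left to a statistical analysis plan, which is not shown here. Much of that stands: the absence of k or of an interval would not by itself be a finding. But the protocol is not silent. It names one summary and presents it as the account of accuracy as well as consistency, and that summary does not measure the precision the study was sized for.

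Three stronger readings are tempting, and the documents do not support them.
- A reader might infer that the trial cannot show whether it met its precision target. It can: intervals can be computed later from the same out-of-fold predictions, and nothing in the protocol prevents this.
- A reader might infer that results will look more precise than they are. At k = 5 or 10 the expected SD is wider than the 95% half-width, so the error is towards understating precision, and at k = 5 the excess is modest (0.038 against 0.034 for accuracy).
- A reader might infer that an interval built from SD/sqrt(k) would cover badly. The protocol proposes no such interval. With a t quantile on k − 1 degrees of freedom, simulated coverage is about 94.5% for sensitivity and 95% for specificity and accuracy. Overlapping training sets remain a reservation in principle, but their effect has not been quantified.

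**Conclusion.** The point holds as a mismatch between the stated summary and the sizing target. For accuracy at N = 600, the expected fold SD is 0.038 with five folds and 0.054 with ten, against a fixed 95% half-width of 0.034. Read as uncertainty, the SD is 1.14 and 1.61 times that half-width, and the factor is set by k alone. At N = 600 the whole-sample half-widths for sensitivity (0.037) and specificity (0.047) would both meet the 0.05 target under the plan's assumptions, but the fold SD would not show this.

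The figures rest on the plan's assumed performance and prevalence, one out-of-fold prediction for each of 600 patients, independent binomial outcomes and equal stratified folds. They leave out variation between the fitted fold models. The protocol also aims to separate normal, osteopenia and osteoporosis; a three-class accuracy would have a different value, but the sqrt(k) relation would be the same. The documents give no inputs from which to size the effect for MAE, PCC or AUPRC.

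**What to change.** In Methodology f), state the number of folds and keep the fold mean and SD explicitly as a description of stability. Then add that the out-of-fold predictions of all patients are pooled, and that each metric, together with the sized sensitivity and specificity, is computed once on the full sample with a 95% confidence interval: Wilson or exact for proportions, and a bootstrap that resamples patients for MAE, PCC and AUPRC. The intervals for sensitivity and specificity can then be set directly against the 0.05 target.

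The protocol should also state the limits of these intervals. They are conditional on the fitted fold models, they do not cover retraining variability or the optimism from choosing the best of several architectures, and pooling across fold models can slightly shift PCC or AUPRC.

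The cost is a few sentences of text and a few lines of code, with no new data.

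### The plan selects a CNN strategy and evaluates it on the same k-fold data; if the winner's own score is reported as its performance, that score is optimistic in expectation

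*Protocol*

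**What the plan says.** All references are to the protocol.

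- **Methodology e), Data Interpretation:** one dataset serves both purposes: "The refined dataset will serve as the foundation for training and evaluating our AI model". The model is a regression of BMD, "aiming to identify potential cases of osteopenia, osteoporosis, and normal".
- **Methodology f), Statistical Analysis:** the analysis starts from a closed dataset: "Upon finalizing the dataset, our statistical analysis will concentrate on evaluating the artificial intelligence" model. The evaluation method is cross-validation: "we will implement k-fold cross-validation techniques, providing a framework for evaluating our model across various subsets of data". Its output is to "calculate mean values and standard deviations for each performance metric, offering a comprehensive understanding" of predictive accuracy and consistency. The metrics are MAE, PCC, AUPRC and accuracy. The section closes with the selection step: "The culmination of our analysis will involve a comparative review of different CNN architectures and training methodologies to determine the most effective strategy".
- **Objectives:** public and local images form a single "dataset of X-ray images sourced from publicly available domains and local health facilities". Objective b) promises validation on diverse data but assigns no patients to it.
- **Flow Chart:** the public data have one stated use: "Initial algorithm with publicly available data".

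Not stated: the number of folds, the number of candidate strategies, the metric that decides between them, any nesting, and which score will be quoted for the strategy chosen.

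**The concern.** A cross-validated score is the true performance plus sampling error. When several strategies are scored on the same patients and the best is kept, the choice favours strategies whose error happened to be in the good direction. The winner's score therefore overstates, on average, what that strategy achieves. The effect falls on the winner's score for the metric that decided the choice, and on other metrics as far as they correlate with it. The scores of all candidates shown together as a comparison are not biased in this way.

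The order in Methodology f) is to evaluate by k-fold and then determine the best strategy, and no estimate separate from that choice is named. The results are meant to guide physicians on whether a DEXA scan is warranted (Rationale; Utilization of Results), so the figure quoted for the chosen strategy should not carry a selection effect that is cheap to remove.

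**Working it through.** **1. Is anything kept out of the selection?**

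- Public data: pooled into the same dataset in Objectives and used for an initial algorithm in the Flow Chart. Neither place reserves them for testing.
- DEXA comparison with specialist review (Methodology e): no separate patients are named, and DEXA is already the ground truth for training.
- Objective b): an aim with no test set attached.

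**2. Inputs from the protocol (Methodology b).** Sensitivity 0.911, specificity 0.689, prevalence 0.373, precision 0.05, 95% confidence, target 600. The stated sample sizes reproduce:

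- N_sen = 1.96² × 0.911 × 0.089 / (0.05² × 0.373) = 334.01, rounded up to 335.
- N_spec = 1.96² × 0.689 × 0.311 / (0.05² × 0.627) = 525.13, rounded up to 526.

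These formulas treat the algorithm as fixed and have no term for selection. The 0.05 precision concerns sensitivity and specificity, so it is no yardstick for the optimism below.

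**3. Assumptions, not in the protocol.** M = 2 to 20 candidates; correlation ρ = 0.3 to 0.8 between their score errors, since they share patients; true accuracies that vary with SD τ = 0, 2 or 5 points; and accuracy taken as two-class, because the protocol does not define it for three groups:

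- accuracy = 0.911 × 0.373 + 0.689 × 0.627 = 0.772
- standard error s = √(0.772 × 0.228 / 600) = 1.71 points

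**4. Optimism of the winner's score.** The error shared by all candidates does not affect the ranking. With E_M the expected maximum of M independent standard normals (0.564, 1.163, 1.539 and 1.867 for M = 2, 5, 10 and 20):

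optimism = E_M × s²(1 − ρ) / √(τ² + s²(1 − ρ))

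Example, M = 20, ρ = 0.3, τ = 0: 1.867 × 1.71 × √0.7 = 2.7 points. Monte Carlo runs with 200,000 draws per cell agree. Results in accuracy points for ρ = 0.3 / 0.5 / 0.8:

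| True spread | M = 2 | M = 5 | M = 10 | M = 20 |
|---|---|---|---|---|
| SD 0 | 0.81 / 0.68 / 0.43 | 1.67 / 1.41 / 0.89 | 2.20 / 1.86 / 1.18 | 2.67 / 2.26 / 1.43 |
| SD 2 points | 0.47 / 0.35 / 0.16 | 0.97 / 0.73 / 0.32 | 1.28 / 0.96 / 0.42 | 1.56 / 1.17 / 0.51 |
| SD 5 points | 0.22 / 0.16 / 0.07 | 0.46 / 0.33 / 0.13 | 0.61 / 0.44 / 0.18 | 0.74 / 0.53 / 0.22 |

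The range is 0.07 to 2.7 points. Where candidates truly differ (SD 2 or 5), 21 of 24 cells are below 1 point.

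**5. Sensitivity to the metric.** With 5 to 20 candidates and SD 0 or 2, the range is 0.4 to 3.1 points at accuracy 0.60 and 0.2 to 1.9 points at 0.90. If MAE decides (equal candidates, normal errors), its relative standard error is √(π/2 − 1)/√600 = 3.08%. Multiplied by 0.52 (M = 5, ρ = 0.8) to 1.56 (M = 20, ρ = 0.3), the winner's MAE is 1.6% to 4.8% too low.

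**6. Offset from smaller training folds.** With 5 folds, each model trains on 480 of 600 patients. If G = 2 to 5 accuracy points remain to be gained beyond 600 patients (assumed, with the gap shrinking as the square root of n), the score is too low for a model refitted on all 600 by G × (√(600/480) − 1) = 0.118 × G = 0.24 to 0.59 points. Net: 0.07 − 0.59 = −0.52 to 2.67 − 0.24 = +2.43 points.

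**7. Does nesting remove the selection term?** Plain and nested 5-fold selection were simulated with 600 patients and 4,000 trials in each of 18 cells (M = 5, 10, 20; SD 0 or 2). The plain winner's score was biased by 0.34 to 2.72 points. Nested outer-fold scores were biased by −0.03 to +0.07 (Monte Carlo standard error about 0.03 to 0.04).

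**The case against.** The strongest reply is that this is silence, not error. Nesting and the final reporting estimate are often left to an SAP, which is not at hand. Methodology f) does not exclude nesting, does not say that candidates are ranked on these k-fold scores, and does not say that the winner's score will be the headline figure. That stands as a limit: a reader might infer that the plan commits to reporting an inflated figure, and the document does not support that. It does not dispose of the point. The section fixes a framework, its output and a closing selection, and nested cross-validation is a concretely better method than the one named.

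The reply on size also stands in part. Every driver of the magnitude is assumed, and 2.7 points requires 20 candidates that are all truly equal. A reader might take that as the expected inflation; the table shows that it is the extreme. The protocol sets no performance threshold, so no conclusion can be shown to change.

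Nor is the sign settled for the model that would be used. The optimism is relative to performance at the fold training size. For a model refitted on all patients, the training-size offset can cancel or exceed it. Outer folds of the same size carry the same offset, however, so it does not explain away the gap between plain and nested scores.

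**Conclusion.** The point holds in conditional form and should be fixed. One dataset serves training and evaluation, k-fold is the only framework named, and the analysis ends by choosing a strategy with nothing named outside that choice. If the chosen strategy's own k-fold score is reported as its performance, it is optimistic in expectation at the fold training size. The effect is about 0.1 to 2.7 accuracy points under the stated assumptions, and mostly under 1 point when candidates truly differ. For a model refitted on all 600 the net is roughly −0.5 to +2.4 points, so its direction is not certain. The direction of the selection effect is firm; its size is only illustrative, because the protocol gives neither the number of candidates nor their correlation, spread or accuracy definition.

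Three stronger readings are not supported: that the plan states that it will report the winner's score, that the inflation is known to be large, and that the sample size is wrong.

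**What to change.** In Methodology f):

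1. Use nested cross-validation, for example 5 outer and 5 inner folds. Draw the folds by patient: the retrospective phase in Methodology c) collects all spine and hip images, so one patient may contribute several.
2. Choose architecture and training method in the inner loop on one named metric, for example MAE, since the model is a regression.
3. Report outer-fold means and SDs as the performance of the model-selection procedure. Outer folds may pick different architectures, so these figures do not belong to one fixed model.
4. Name the final strategy by applying the same selection rule to the full dataset, and refit it on all patients.
5. Report the architecture comparison separately, labelled as model selection and not as the final model's performance.

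Generalizability across settings (objective e) is a separate matter that random nested folds do not address.

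**Cost:** no new patients. For 10 candidates, plain 5-fold takes 10 × 5 = 50 training runs. Nesting takes 10 × 5 × 5 + 5 = 255, and the full-data selection adds 50, so about 305 runs plus one refit. This has to fit the four-month Flow Chart. The reported metrics will be slightly less favourable.
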